6.2. Allowed and disallowed therapy

Allowed concomitant therapy

During the study, if a patient develops infectious complications of underlying disease, the administration of broad-spectrum antibiotics is permitted, in accordance with accepted medical practice, local and national protocols, and in compliance with the legislation of Ukraine.

The patients participating in this trial may receive the concomitant therapy continuously used to manage their comorbidities and life-threatening conditions (such as antibiotic therapy as needed).

It is allowed to continue replacement therapy with previous IVIG or SCIG products during the screening period.

If vaccination is required, in accordance with legal requirements, the use of inactivated vaccines, vaccines against meningococcal infection and vaccines against influenza is permitted (as decided by the Responsible Investigator, taking into account the patient's clinical condition).

The use of contraceptives is allowed in women of childbearing potential.

Disallowed concomitant therapy.

During patients' participation in the clinical study, the use of the following medicinal products is disallowed:

- any agents with potential immunostimulatory or immunosuppressive effects;
- anticoagulants;
- all live vaccines;
- other human immunoglobulin products (with the exception of those allowed during the screening period) blood products;
- any agents, which, in the Investigator's judgement, could confound study results.

6.3 Procedures

6.3.1 Informed Consent signing

A written informed consent to participation in the study shall be obtained from all patients enrolled in the study, or from the patient's legally authorised representative, or from both parents of minors prior to start of any study procedures.

Prior to enrolment in the study, the patient shall have his/her rights and responsibilities related to participation in the study explained to him/her. The patient or his/her legally authorised representative should know that he/she may refuse to take part in the study at any time with no negative impact on his/her further treatment. He/she shall also be informed that the fact of his/her participation in the study is strictly confidential and that any clinical trial documents will only use his/her initials and subject identification number.

The Investigator/study personnel shall explain to the patient that his/her personal data obtained during the study will be used for statistical processing of the study results and for reporting purposes; this data may also be discussed by the persons conducting the study and may be disclosed to representatives of state regulatory authorities during clinical audits.

The patient or his/her legally authorised representative shall have sufficient time to consider his/her participation in the study and to ask the Investigator any questions he/she might have. The Investigator is obliged to explain in detail the sections of Informed Consent where the patient has questions, and provide clear instructions regarding the safeguards and patient's actions in the event of risks for the patient in the course of the CT. The Investigator shall not attempt to coerce the patient with an intent to influence his/her decision.

If the patient or his/her legally authorised representative decides to take part in the study, he/she shall personally complete and sign 2 copies of Informed Consent Form (ICF). One original copy of Informed Consent is issued to the patient to keep for his/her records, and the other remains in the Investigator's file.

The fact of informed consent discussion shall be documented in the patient's medical record and the CRF with an indication of the signature date.

The screening and inclusion of the patient into the clinical study are performed only after signing the Informed Consent Form.

In the event changes are made to the ICF during the clinical study, and if such changes are not related to the safety or well-being of the study subject, a repeated signing of the form by already included patients is not required.

For patients younger than 18 years, ICF signing is envisaged under a procedure identical to the one above, with mandatory signing of the ICF by both parents of the patient.

6.3.2 Entering information into the Patient's Diary

- The use of Patient's Diary (PD) is envisaged as part of the study. The diary is intended for entering information regarding self-administration of the IMP by the patient.
- Investigators conduct a training for each patient on how to work with the Patient's Diary.
- Filling the PD begins with the C2W6 Visit after administration of the IMP and ends after the last administration of the IMP;
- The patient receives a printed brochure (Patient Diary) signed off by the Responsible Investigator.
- The data into the diary are entered by the patient, patient's legally authorised representative, both patient's parents or one of their parents (for children from 0 to 12 years of age inclusive).
- The patient/legally authorised representative/parents of the patient enter the following data after each home-based administration of the IMP: **date and time of start and end of administration, dose, infusion rate, administration points, volume of administration into each point, the batch and the number of vials of each batch, the presence of adverse events, data on antibiotic therapy and concomitant therapy, the presence of infections**.
The data entered shall be carefully checked by the patient.
- The Investigator is obliged to check the completion of the diary at the nearest on-site visit, make a copy of checked PD pages, and enter the data into the eCRF.
- The correctness of transferring data into the eCRF is checked by the Monitor.

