4. STUDY DESIGN

4.1. Endpoints

Safety and tolerability endpoints

- Frequency of adverse events
- Incidence of adverse reactions to IMP
- Frequency of serious adverse reactions
- Emergence of treatment-emergent adverse events
- The frequency of treatment-emergent adverse events related to infusion rate
- The incidence of administration site reactions
- The frequency of clinically significant deviations in vital signs (blood pressure, body temperature, pulse rate and respiratory rate)
- The frequency of clinically significant deviations in laboratory findings (complete blood count, biochemical findings, markers of intravascular haemolysis, and coagulation parameters)

Safety data are also assessed separately in children and adolescents (after an interim assessment in adults) and compared with the adult data.

Primary pharmacokinetic endpoint:

Mean threshold (trough) plasma concentration of total IgG prior to the next administration of the product, when reaching steady state (after 4 months of treatment), assessed over 6 months.

Primary pharmacokinetic variable:

The monthly trough IgG levels, measured after 4 months of treatment with the IMP, prior to the next infusion, once every 4 weeks, over 6 months, did not fall below the trough levels of the previous therapy with SCIG or IVIG (BIOVEN).

Secondary pharmacokinetic endpoints

These endpoints are tested in the subgroup of subjects aged over 18 years who received treatment with BIOVEN prior to their enrolment in the study and, respectively, throughout the screening period:

- To confirm or calculate the IMP dose adjustment factor when converting from previous IVIG therapy with BIOVEN;

Tested in a subgroup of at least 20 adult patients with PID after approximately 4 months of treatment with the IMP BP-SCIG 20%:

- Area under the concentration-time curve (AUC)
- Maximum concentration (Cmax)
- Time to reach maximum concentration (Tmax)
- The threshold levels of total IgG during the dose titration phase (the dose-effect dependence)
- the *in vivo* elimination half-life
- the elimination constant
- serum clearance
- volume of distribution
- incremental recovery

Secondary endpoints are transformed into corresponding variables.

Primary efficacy endpoint:

Primary efficacy endpoint: The number of serious bacterial infections per subject per year (in order to achieve less than 1.0 infections/subject/year)

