- Interim administration 1(C9W34) – Week 34, IMP administration in the home;
- Interim administration 2(C9W35) – Week 35, IMP administration in the home;
- Interim administration 3(C9W36) – Week 36, IMP administration in the home.

Cycle 10:

- Visit 13 (C10W37): **On-site visit** – Week 37 of IMP administration;
- Interim administration 1(C10W38) – Week 38, IMP administration in the home;
- Interim administration 2(C10W39) – Week 39, IMP administration in the home;
- Interim administration 3(C10W40) – Week 40, IMP administration in the home.

Cycle 11:

- Visit 14 (C11W41): **On-site visit** – Week 41 of IMP administration;
- Interim administration 1(C11W42) – Week 42, IMP administration in the home;
- Interim administration 2(C11W43) – Week 43, IMP administration in the home;
- Interim administration 3(C11W44) – Week 44, IMP administration in the home.

Cycle 12:

- Visit 15 (C12W45): **On-site visit** – Week 45 of IMP administration;
- Interim administration 1(C12W46) – Week 46, IMP administration in the home;
- Interim administration 2(C12W47) – Week 47, IMP administration in the home;
- Interim administration 3(C12W48) – Week 48, IMP administration in the home.

Cycle 13:

- Visit 16 (C13W49): **On-site visit** – Week 49 of IMP administration;
- Interim administration 1(C13W50) – Week 50, IMP administration in the home;
- Interim administration 2(C13W51) – Week 51, IMP administration in the home;
- Interim administration 3(C13W52) – Week 52, the last IMP administration in the home.

Data are entered into the eCRF in accordance with the Schedule of Study Procedures (see Table 4.2.1).

The patient/parents of the patient/legally authorised representative fill(s) in the patient's diary after each interim administration of the cycle starting with Visit C2W6.

The Investigator shall contact the patient/parents/legally authorised representative by telephone at least once per interim IMP administration period of each Cycle, in order to monitor/remind them about IMP administration in the home, filling in the patient diary, and tracking of any potential adverse reactions. The fact of the telephone contact shall be recorded in the "Telephone Contact Form" provided by the Sponsor.

Pharmacokinetic assessment phase

Determination of threshold (trough) IgG levels

Prior to the start of the phase, each patient who has completed 4 months of treatment must have a monthly assessment of threshold IgG level (immediately before the administration).

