6. TREATMENT OF SUBJECTS

6.1. Treatment regimen

The IMP shall be administered subcutaneously.

All patients will receive the investigational medicinal product BP-SCIG 20%, solution for subcutaneous administration manufactured by BIOPHARMA PLASMA LLC.

The IMP BP-SCIG 20% shall be administered at the frequency of once a week for 52 weeks, subcutaneously using a CRONO S-PID4 infusion pump.

The dosing regimen shall be designed to achieve a trough IgG level (at least 5–6 g/L), which will be measured before the next infusion.

Efforts must be taken to maintain serum IgG within the reference range for the corresponding age group of patients.

Individual dose selection and adjustment may be required for each patient, depending on the pharmacokinetic response (IgG level) and clinical response. Threshold levels must be assessed in combination with the incidence of infectious episodes. To reduce the risk of infection, it may be necessary to increase the dose and aim to achieve higher trough IgG levels.

A loading dose of IMP may be required (at the Investigator's decision): at least 0.2–0.5 g/kg (1.0–2.5 mL/kg) of body weight. This dose is distributed across several days, with a maximum daily dose of 0.1 to 0.15 g/kg.

After achieving a steady-state (minimal) level of IgG, maintenance doses are administered at repeated intervals (approximately once a week) to achieve a cumulative monthly dose of 0.4–0.8 g/kg. Each single dose must be administered to different anatomical locations.

Since the bioavailability of SCIGs is 30 % lower than that of IVIGs, partly due to binding to the extracellular matrix and cleavage by tissue enzymes (Wang et al. 2008; Berger et al. 2013), a dose adjustment factor of 1.37 will be used to convert the IVIG dose to the SCIG dose. This is based on historical data for bioequivalence evaluation of these administration routes (Wasserman et al. 2010, 2011; Berger et al. 2011) and meets the requirements of the US Food and Drug Administration (US FDA), according to which the SCIG doses must be adjusted to ensure an equivalent AUC for total IgG compared to previous IVIG therapy. Dose calculation for patients who received IVIG prior to the start of their participation in the study (John W Sleasman et al. 2019):

The initial dose of SCIG

$$\text{IgG} = \frac{\text{Previous IVIG dose (in grams)} \times 1.37}{\text{Number of weeks between IVIG administrations}}$$

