The dose adjustment factor of 1.37 will be evaluated in an interim pharmacokinetic (PK) analysis and modified as needed.

The first four IMP administrations are for training purposes, during which the investigational medicinal product BP-SCIG 20% for subcutaneous administration will be administered by a responsible member of the study team in a hospital setting and by the patient/legally authorised representative or parents after an appropriate training and in compliance with aseptic/antiseptic precautions under the supervision of responsible and trained members of the study team.

The study doctor prescribes the dose and rate of subcutaneous administration of the IMP for home-based use. The patient/their legally authorised representative or parents will be instructed by the Investigator regarding the use of the CRONO S-PID4 infusion pump, the administration technique, filling out the patient's diary, recognition of adverse reactions and measures to be taken in the event of adverse reactions.

Prior to use, the solution must be at room temperature and remain outside the refrigerator for at least 30 minutes. Turbid solutions and/or solutions with sediment must not be used.

To administer the IMP, a CRONO S-PID4 infusion pump and a dedicated single-use infusion set are used.

The IMP BP-SCIG 20% can be administered in sites with ample subcutaneous fat, such as the abdomen, the shoulder, and lateral thigh.

The IMP BP-SCIG 20% is administered subcutaneously using a CRONO S-PID4 infusion pump. Multiple lines can be used for administration into several sites simultaneously. It is recommended to use an initial infusion rate of 10 mL/h/line. If well tolerated, the infusion rate may be increased by 5 mL/h/line at each subsequent administration. The recommended maximum rate is 25 mL/h/line. The amount of product infused into a certain site must not exceed 25 mL. In infants and children, the administration site can be rotated every 5–15 mL. For adults, doses above 30 mL can be divided into several doses, in accordance with the patient's preferences. There are no limitations regarding the number of injection sites.

Hypersensitivity to active ingredient or any of the excipients is a contraindication.

The product must not be administered via the intravascular route. If BP-SCIG 20% is inadvertently administered into a blood vessel, the patient may develop shock. In the event of shock, standard treatment of shock must be instituted.

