13.5. Data collection: Patient's Diary (PD)

The Patient's Diary is kept personally by the patient in paper form to record all necessary information regarding the self-administration of the IMP as part of the study.

- The diary is intended for entering information regarding self-administration of the IMP by the patient.
- Investigators conduct a training for each patient on how to work with the PD.
- Completion of the PD begins after the first interim administration of the IMP in the home and ends after the last interim administration of the IMP during 2 days;
- The data are entered into the diary by the patient/legally authorised representative/parents.
- The following shall be recorded in the diary: **the date and time of the start and end of administration, the dose, infusion rate, administration points, volume of the IMP administered at each site in mL, the number of IMP vials used, the presence of adverse events). The data entered shall be carefully checked by the patient/legally authorised representative/parents.**
- The Investigator is obliged to check the completion of the diary at the Visit and transfer the data to the eCRF.

The Diary is required for:

- Provision of data collection in accordance with the Protocol;
- Ensuring the quality collection of data on the safety of the IMP
- Reflection of the patient's treatment compliance
- Facilitating the effective and complete processing of data, their analysis, and reporting based on CT results.

The Monitor shall also check the information entered into the PD for its consistency with the eCRF. If any discrepancies are identified, the Monitor must discuss this with the Investigator and ensure that the training for the patient on how to use the diary was conducted properly.

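### The patient diary starts at Week 6 and covers home infusions only, so reactions that begin after the patient leaves the site have no diary entry for 16 of 52 infusions, including all of Cycle 1

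*Protocol*

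**What the plan says.** Three sections of the protocol set the diary rule, and they agree on when it starts.

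- Section 6.3.2: "Filling the PD begins with the C2W6 Visit after administration of the IMP and ends after the last administration of the IMP". Patients or parents "enter the following data after each home-based administration of the IMP".
- Section 4.2: the family completes the "patient's diary after each interim administration of the cycle starting with Visit C2W6".
- Section 13.5: "Completion of the PD begins after the first interim administration of the IMP in the home". The same sentence ends with a reference to two days whose meaning is unclear.

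Table 4.2.1 shows two ways of registering adverse events and reactions. At on-site infusions the study doctor does it as a mandatory item. At home infusions the patient writes it in the diary.

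The safety endpoints in Section 4.1 include administration-site reactions and "The frequency of treatment-emergent adverse events related to infusion rate". Section 6.3.21 presents the diary as a main source for capturing every change in the patient's health. The same section has the Independent Safety Committee review the first 10 adults after at least four infusions before children may enter, and each age group after its first four infusions before the next one opens.

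**The concern.** A reaction that starts during an on-site infusion, or in the short observation afterwards, is seen by staff. One that starts later that day or the next is not, and the patient has no diary page for it. Sections 2.3 and 6.1 require at least 20 minutes of observation after an infusion, or the first hour after the first infusion for patients who are naive, have switched product or have had a long gap. Section 2.3 itself describes aseptic meningitis as beginning from a few hours to two days after treatment, and says local reactions may be frequent.

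At stake are two endpoints whose events are collected in one way after 36 infusions and in another after 16. The safety gate is affected too: none of the first four infusions has a diary entry. Section 2.3 says some reactions may be more frequent at first exposure or, rarely, on a change of product, and patients entering this study are either naive or switching.

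**Working it through.** **Count of infusions.** Section 6.1: "The IMP BP-SCIG 20% shall be administered at the frequency of once a week for 52 weeks", so 52 infusions. Section 4.2 gives 13 main on-site visits and 3 on-site interim administrations:

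- On site: 13 + 3 = 16. The visit list confirms this: Weeks 1 to 4 (4 infusions) plus Weeks 5, 9, 13, …, 49 (12 infusions), 4 + 12 = 16.
- At home, with a diary entry: 52 − 16 = 36; the first is Week 6.
- Without a diary entry: 16/52 = 30.8%. With one: 36/52 = 69.2%.
- By cycle: 0 of 4 in Cycle 1; 3 of 4 in each of Cycles 2 to 13 (12 × 3 = 36).

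**Where a late reaction is recorded after an on-site infusion.**

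| Infusion | Next opportunity to record it |
|---|---|
| Weeks 1–4 | Next on-site visit, about 7 days later (Week 5 for the fourth infusion) |
| Week 5 and the first infusion of Cycles 3–13 | A diary entry made for the following home infusion, the telephone contact in that cycle's interim period, or the next on-site visit 4 weeks later |

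Section 4.2 describes the telephone contact in terms of home administration, so it does not clearly apply in Cycle 1, where all four infusions are on site.

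**Relation to infusion rate.** Section 6.1 starts at 10 mL/h/line, recommends a maximum of 25, and says that, if tolerated, "the infusion rate may be increased by 5 mL/h/line at each subsequent administration". The step is optional and no end of escalation is fixed. On the fastest permitted path the rates are 10, 15, 20 and 25 at Weeks 1 to 4. The slower paths below are assumptions that show the range.

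| One step every … infusions | Rate at Week 6 | First infusion at 25 | Infusions below 25 | Of these, with a diary entry |
|---|---|---|---|---|
| 1 (fastest) | 25 | Week 4 | 3 | 0 (0%) |
| 2 | 20 | Week 7 | 6 | 1 (17%) |
| 3 | 15 | Week 10 | 9 | 3 (33%) |
| 4 | 15 | Week 13 | 12 | 6 (50%) |

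Only on the fastest path do all infusions below the maximum rate lack a diary entry.

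**Item lists.** Section 6.3.2, and the list of diary data transferred to the eCRF in Section 4.9, include infections, antibiotic therapy and concomitant therapy. Section 13.5 lists adverse events but none of these three. Infections and antibiotic use feed secondary efficacy endpoints in Section 4.1.

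**The case against.** The best defence is that this is a coherent design. The diary exists to document self-administration, and where staff are present staff record. The first four infusions are supervised throughout, the doctor must register events at each, and another doctor visit follows within about a week. That is the closest physician contact in the trial. From Cycle 2 a telephone contact is made at least once in each interim period, expressly to track possible adverse reactions. Patients are trained to recognise reactions, an unscheduled visit can be made for a new event, and the onset date is recorded, which helps to assign a late reaction to its infusion.

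Most of this stands, and it rules out several stronger readings that a reader might draw:

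- *That 16 infusions have no safety record.* They have a doctor's record; what is missing is the patient's own record after leaving.
- *That the first infusions are the least well recorded, so incidence reads low.* The protocol gives no look-back period for the diary, apart from the unclear two-day phrase, so it does not show how much better the diary captures late reactions. Nor does it give the timing of local reactions.
- *That the capture method changes exactly when rate escalation ends.* The change follows the move to home dosing. Even on the fastest path Week 5 is a further on-site infusion, and slower paths run on into the diary period.
- *That a planned comparison by rate or setting is biased.* None is planned: Section 9.5 describes adverse events by frequency and percentage for the group. The 12 later on-site infusions would also allow some comparison of settings.

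The defence does not answer the narrower point. After an on-site infusion, a delayed reaction depends on recall or on a contact made for another purpose, and the committee's review relies on just such infusions.

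**Conclusion.** The point holds as a gap in the capture of delayed reactions. For 16 of 52 infusions (31%), including all four in Cycle 1, no diary entry is made, and the required observation ends 20 minutes to one hour after the infusion. The counts follow directly from the visit list and rest on no assumption beyond the planned schedule being followed.

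The gap touches administration-site reactions, rate-related treatment-emergent events and the safety review that gates the entry of children. For a patient reviewed at exactly four infusions, there are no diary data at all, although Section 6.3.21 counts on the diary for completeness. A patient who is past Week 6 at the time of review would have some, but for later infusions only.

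The size and direction of any effect on the reported frequencies cannot be derived from the protocol. An overlap of rate with capture method that leaves every lower-rate infusion without a diary occurs only on the fastest permitted escalation. The point is worth acting on because the remedy is cheap, not because a bias has been shown. The shorter item list in Section 13.5 is a separate, minor inconsistency to correct in the same amendment.

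**What to change.** Issue the diary at Visit 4 (C1W1) and have it completed after every infusion, on site and at home, with the same items and one stated look-back period. Keep the doctor's registration of adverse events at visits as it is. Amend Sections 4.2, 6.3.2 and 13.5 and the corresponding cells of Table 4.2.1. Replace the unclear two-day wording in Section 13.5 with the chosen look-back period, and make its item list match Section 6.3.2 (infections, antibiotic therapy, concomitant therapy).

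Diary coverage would rise from 36 to 52 of 52 infusions. The cost is 16 more short entries per patient and diary training moved forward to the first infusion. No visits or staff are added, and no dose, infusion rate or observation rule changes.
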